**1.0 Safety Endpoints (continued)**

Vascular Access Site and Access Related Complications	
Major vascular complication	1) Any aortic dissection, aortic rupture, annulus rupture, left ventricle perforation, or new apical aneurysm/pseudoaneurysm OR 2) Access site or access-related vascular injury (dissection, stenosis, perforation, rupture, arterio-venous fistula, pseudoaneurysm, hematoma, irreversible nerve injury, compartment syndrome, percutaneous closure device failure) leading to death, life-threatening or major bleeding, visceral ischemia, or neurological impairment OR 3) Distal embolization (noncerebral) from a vascular source requiring surgery or resulting in amputation or irreversible end-organ damage OR 4) The use of unplanned endovascular or surgical intervention associated with death, major bleeding, visceral ischemia or neurological impairment OR 5) Any new ipsilateral lower extremity ischemia documented by patient symptoms, physical exam, and/or decreased or absent blood flow on lower extremity angiogram OR 6) Surgery for access site-related nerve injury OR 7) Permanent access site-related nerve injury
Minor vascular complication	1) Access site or access-related vascular injury (dissection, stenosis, perforation, rupture, arterio-venous fistula, pseudoaneuysms, hematomas, percutaneous closure device failure) not leading to death, life-threatening or major bleeding*, visceral ischemia, or neurological impairment OR 2) Distal embolization treated with embolectomy and/or thrombectomy and not resulting in amputation or irreversible end-organ damage OR 3) Any unplanned endovascular stenting or unplanned surgical intervention not meeting the criteria for a major vascular complication OR 4) Vascular repair or the need for vascular repair (via surgery, ultrasound-guided compression, transcatheter embolization, or stent-graft)
Percutaneous closure device failure	Failure of a closure device to achieve hemostasis at the arteriotomy site leading to alternative treatment (other than manual compression or adjunctive endovascular ballooning)

\*Refer to VARCII bleeding definitions

VALVE DYSFUNCTION REQUIRING REPEAT PROCEDURE
---

Any valve dysfunction that requires repeat procedure (eg, balloon valvuloplasty, TAVR, snare repositioning, placement of vascular plug paraavalvular leak, or surgical AVR)
---

Note: Repeat procedures are reported on the appropriate eCRF (Surgical Intervention or Catheter Reintervention)

**2.0 Other Related Complications**

Complication	Definition
Conversion to open surgery	Conversion to open sternotomy during the TAVR procedure secondary to any procedure-related complications
Unplanned use of cardiopulmonary bypass	Unplanned use of CPB for hemodynamic support at any time during the TAVI procedure
Coronary artery obstruction	Angiographic or echocardiographic evidence of a new, partial or complete, obstruction of a coronary ostium, either by the TAV prosthesis itself, the native leaflets, calcifications, or dissection, occurring during or after the TAVR procedure.
Ventricular septal perforation	Angiographic or echocardiographic evidence of a new septal perforation during or after the TAVR procedure
Mitral valve apparatus damage or dysfunction	Angiographic or echocardiographic evidence of new damage (chordae, papillary muscle, or leaflet) to the mitral valve apparatus or dysfunction (eg, restrictions due to the TAV of the mitral valve during or after the TAVR procedure
Cardiac tamponade	Evidence of new pericardial effusion associated with hemodynamic instability and clearly related to the TAVI procedure
Prosthetic valve thrombosis	Any thrombus attached to or near an implanted valve that occludes part of the blood flow path, interferes with valve function, or is sufficiently large to warrant treatment. Valve-associated thrombus identified at autopsy in a patient whose cause of death was not valve related should not be reported as valve thrombosis.
Valve migration	After initial correct positioning, any observed movement (upward or downward) of the TAV within the aortic annulus from its initial position, with or without consequences.
Valve embolization	The TAV moves during or after deployment such that it loses contact within the aortic annulus
Ectopic valve deployment	Permanent deployment of the TAV in a location other than the aortic root
TAV in TAV deployment	Additional valve prosthesis is implanted within a previously implanted TAV because of sub-optimal device position and/or function, during or after the index procedure.
Hemolysis	Red cell destruction confirmed by lab data Minor hemolysis: No intervention required Major hemolysis: Requires intervention (eg, iron supplements, transfusion, invasive intervention).
Frame fracture	Visual evidence on radiography or at explant of loss of contact between elements (cells) of the stent. Minor frame fracture: Does not require intervention, or is not associated with prosthetic valve dysfunction. Major frame fracture: Intervention required (eg, reoperation, catheter re-intervention) or is associated with prosthetic valve dysfunction

**2.0 Other TAVR-Related Complications (continued)**
**PROSTHETIC VALVE ENDOCARDITIS**

Any of the following:

1) Fulfillment of the following Duke criteria for definite endocarditis:

- Histologic and/or microbiologic evidence of infection at surgery or autopsy, or
- 2 major criteria, or
- 1 major criteria or 3 minor criteria, or
- 5 minor criteria

Major and minor criteria are as follows:

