### **3.3.27 Clinical Events Committee**

A Clinical Events Committee (CEC) will provide independent medical review and adjudication of adverse event data used in the safety assessment of the investigational device. The CEC will adjudicate all deaths and safety endpoint-related adverse events reported by the investigators. The CEC will follow the recommendations of VARC II for classifying adverse events that relate to clinical safety endpoints. The analysis of the trial safety data will be based on CEC adjudicated events. Safety endpoint definitions are provided in APPENDIX V: DEFINITIONS: SAFETY ENDPOINTS AND EFFICACY EVENTS.

The CEC members will be free from bias towards the trial and will be independent from both the trial and investigators and Medtronic. The committee will consist of at least 3 independent experts (non-Medtronic employed physicians) with expertise relevant to the trial. This may include experience in the areas of:

- Cardiac surgery
- Interventional cardiology
- Neurology
- Electrophysiology

A CEC charter will be developed and approved by Medtronic prior to the first subject enrollment.

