**APPENDIX V: DEFINITIONS: SAFETY ENDPOINTS AND EFFICACY EVENTS**

Definitions of adverse events to be evaluated as clinical safety endpoints, other related complications, and efficacy events are provided in Sections 1.0, 2.0, and 3.0, respectively. The CEC and site investigators will code safety endpoint events according to these definitions, using the associated code list provided on Section 4.0, Event Code List.

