**Major Criteria:**

- Blood cultures positive for Infective Endocarditis (IE)
  - Typical microorganisms consistent with IE isolated from two separate blood cultures, as noted below
    - Viridans streptococci, *Streptococcus bovis*, *Staphylococcus aureus*, or HACEK group
    - Community-acquired enterococci in the presence of a primary focus
  - Microorganisms consistent with IE isolated from persistently positive blood cultures defined as:
    - At least two positive cultures or blood samples obtained >12 hours apart, or
    - All of three, or a majority of four or more separate cultures of blood, the first and last sample obtained > one hour apart
  - Single blood culture positive for *Coxiella burnetii* or an antiphase I Ig antibody titer >1:800
- **Evidence of endocardial involvement**
  - Positive results of echocardiography for IE defined as:
    - Oscillating intracardiac mass on a valve or supporting structures in the path of regurgitant jets or on implanted material in the absence of an anatomic explanation, or
    - Abscess, or
    - New partial dehiscence of a valvular prosthesis
  - New valvular regurgitation (worsening or changing or pre-existing murmur not sufficient)

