**Minor Criteria:**

- **Predisposition:** predisposing heart condition or intravenous drug use
- **Fever:** temperature >38°C
- **Vascular phenomena:** major arterial emboli, septic pulmonary infarcts, mycotic aneurysm, intracranial hemorrhage, conjunctival hemorrhages, and Janeway's lesions
- **Immunological phenomena:** glomerulonephritis, Osler's nodes, Roth's spots, and rheumatoid factor
- **Microbiological evidence:** positive blood culture but does not meet a major criterion (as noted above) or serological evidence of active infection with organism consistent with infectious endocarditis.
- **Echocardiographic findings:** consistent with IE but do not meet a major criterion as noted above

If only 1 major and 1-2 minor criteria are fulfilled, or if only 3-4 minor criteria are fulfilled, the event will be coded as "possible endocarditis"

- 2) Evidence of abscess, paravalvular leak, pus, or vegetation confirmed as secondary to infection by histological or bacteriological studies during a re-operation
- 3) Findings of abscess, pus, or vegetation involving the TAV or surgical bioprosthesis at autopsy

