### Other TAVR-Related Complications

- 150 Conversion to open surgery
- 151 Unplanned use of CPB
- 152 Coronary artery obstruction
- 153 Ventricular septal perforation
- 154 Mitral valve apparatus damage
- 155 Cardiac tamponade
- 156 Prosthetic valve thrombosis
- 157 Valve migration
- 158 Valve embolization
- 159 Ectopic valve deployment
- 160 TAV in TAV deployment
- 161 Major hemolysis
- 162 Minor hemolysis
- 163 Prosthetic valve endocarditis: definite
- 164 Prosthetic valve endocarditis: possible
- 165 Major frame fracture
- 166 Minor frame fracture
- 167 Other TAVR-related complication

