## 6.7. Secondary Safety Endpoints

The following secondary endpoints will be compared between TAVR and SAVR subject cohorts using the appropriate Bayesian version of analysis for comparing proportions. In addition, Kaplan-Meier estimates will be provided.

- The rate of the composite of death, disabling stroke, life-threatening bleed, major vascular complications, or AKI (II or III) at 30 days
- The rate of new permanent pacemaker implantation at 30 days
- The rate of prosthetic valve endocarditis at one year
- The rate of prosthetic valve thrombosis at one year
- The rate of all stroke (disabling and non-disabling) at one year
- The rate of life-threatening bleeding at one year
- The rate of valve-related dysfunction requiring repeat procedure at one year

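### The prosthetic valve endocarditis definition classes the same findings as both definite and possible, because one line says *or* where *and* is needed

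*Protocol*

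**What the plan says.** Protocol Appendix V, section 2.0 (Prosthetic Valve Endocarditis) accepts any of three items: Duke criteria, findings at reoperation, or findings at autopsy. The first item is headed "Fulfillment of the following Duke criteria for definite endocarditis" and lists four alternative routes:

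- histologic or microbiologic evidence at surgery or autopsy;
- two major criteria;
- "1 major criteria or 3 minor criteria";
- five minor criteria.

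After the minor criteria, the same definition adds a rule for weaker evidence: "If only 1 major and 1-2 minor criteria are fulfilled, or if only 3-4 minor criteria are fulfilled", the event is coded as possible endocarditis. The Event Code List (Appendix V, section 4.0) gives the two classes separate codes: 163 for definite, and "164 Prosthetic valve endocarditis: possible".

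The introduction to Appendix V makes this text operative: "The CEC and site investigators will code safety endpoint events according to these definitions". Protocol section 3.3.27 says "The analysis of the trial safety data will be based on CEC adjudicated events" and refers to Appendix V for the definitions. SAP section 6.7 lists "The rate of prosthetic valve endocarditis at one year" among the secondary safety endpoints compared between TAVR and SAVR. The SAP has no endocarditis definition of its own.

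**The concern.** The third Duke route is satisfied by a single major criterion or by three minor criteria. Every combination that the closing note calls possible contains one or the other. An adjudicator who follows the list would code such a case 163; one who follows the note would code it 164. Both would be complying with the protocol.

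The first item of the endpoint definition requires definite Duke criteria, which implies that code 163 is what counts. On that reading, the endocarditis rate in each arm depends on which line the adjudicator applies. The definition also stays in use well beyond one year, because Protocol section 3.3.3.5 and SAP section 6.4 plan Kaplan-Meier estimates through 10 years.

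**Working it through.** No sample size, power or alpha figure is involved. The check enumerates combinations of criteria.

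**Inputs, all from Appendix V section 2.0.** Let M be the number of major criteria met and m the number of minor criteria met. There are two major headings (blood cultures; endocardial involvement) and six minor criteria, so M runs from 0 to 2 and m from 0 to 6, giving 3 × 7 = 21 combinations. The histologic/microbiologic route and the reoperation and autopsy items do not depend on these counts and are left out.

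**Rules.**
- Possible: M = 1 with m = 1 or 2, or M = 0 with m = 3 or 4. This gives (1,1), (1,2), (0,3) and (0,4).
- Definite as written: M ≥ 2, or (M ≥ 1 or m ≥ 3), or m ≥ 5.
- Definite with *and*: M ≥ 2, or (M ≥ 1 and m ≥ 3), or m ≥ 5.

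**Results.**

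| Reading of the third route | Definite | Possible combinations that are also definite |
|---|---|---|
| *or*, as written | 18 of 21 | 4 of 4 |
| *and* | 13 of 21 | 0 of 4 |

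Under *or*, (1,1) and (1,2) qualify through the single major criterion, and (0,3) and (0,4) through the three minor criteria. No combination is possible without also being definite, so code 164 has no content of its own. The two-major and five-minor routes are redundant, since every case with M ≥ 2 already has M ≥ 1 and every case with m ≥ 5 already has m ≥ 3. A list that makes two of its own routes redundant points to a wording slip.

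**If the closing note takes priority.** Removing the four possible combinations from the literal definite set leaves 18 − 4 = 14, against 13 under *and*. The one difference is (1,0), so one major criterion alone is definite, while one major plus one minor is only possible. For example, new valvular regurgitation is listed under the major criteria. With no minor criterion it would be definite. If the prosthesis counts as the predisposition minor criterion, which the documents do not say, the same case is (1,1): definite under the list and possible under the note.

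**Which correction fits.** Replace the third route by one major and k minor criteria, and keep the two-major and five-minor routes:

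| k | Outcome |
|---|---|
| 0 or 1 | overlaps possible at (1,1) and (1,2) |
| 2 | overlaps possible at (1,2) |
| 3 | no overlap, and nothing left between possible and definite |
| 4 | (1,3) unclassified |
| 5 | (1,3) and (1,4) unclassified |

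Only k = 3 fits the note. The unclassified combinations that remain, (0,0), (0,1), (0,2) and (1,0), are 21 − 13 − 4 = 4 in number. They lie below possible, not between the two classes.

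**The case against.** The strongest reply is that the closing note is a specific, mandatory instruction for exactly the disputed combinations. Read as an exception to the general list, it settles all four. The list is labelled as Duke criteria with a citation, and Protocol section 3.3.27 has an independent CEC following VARC II, so an experienced committee may already apply the intended rule. This is plausible, and it limits the practical effect. But no text gives the note priority, section 3.3.27 itself points to Appendix V for the definitions, and site investigators are told to code by the same wording.

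A second reply is that the leftover (1,0) case may never occur. Every subject had severe aortic stenosis, and every case of prosthetic valve endocarditis involves a prosthesis. If either counts as a predisposing condition, at least one minor criterion is always present, and giving the note priority would repair the rule completely. That is fair, but the documents do not settle whether either counts. The four-way overlap does not depend on it.

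Third, if codes 163 and 164 were both counted, the four overlapping combinations would enter the rate either way and only (1,0) could change. That is correct. The four-way overlap matters to the rate only when definite events alone are counted, as the structure of Appendix V implies.

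**Conclusion.** The definition contradicts itself as written: all four possible combinations also meet the definite line. The contradiction is in operative endpoint text, and the document supplies its own answer, because among readings of the form one major and k minor criteria only k = 3 is consistent with the closing note.

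The severity is minor. The endpoint lies outside the hierarchical testing procedure (Protocol section 3.3.3.7; SAP section 6.9), so the primary analysis, type I error and labeling claims are untouched. The documents contain no evidence that an event was miscoded and no basis for estimating how many subjects could be affected. The effect on the rate assumes that definite events alone are counted and that at least some adjudicators follow the list and not the note.

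**What to change.** In Appendix V section 2.0, change the third Duke route so that it requires one major criterion **and** three minor criteria, leaving the closing note as it is. Have the CEC re-check any event coded 163 solely on the literal line. Looking only at code 163 is sufficient because the correction can only narrow the definite class. The trial is not blinded, so the re-check should be done without sight of treatment arm as far as the source documents allow.

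A sentence in the SAP stating which code or codes count in the endpoint would be a convenience. The correction does not depend on it.

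The cost is one word in the definition and a limited re-check, plus the amendment handling in Protocol section 3.3.25: notification to the IRB/EC if administrative, or approval by the IRB/EC and regulators if judged significant. No new data are needed and no analysis method changes.

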**Major Criteria:**

- Blood cultures positive for Infective Endocarditis (IE)
  - Typical microorganisms consistent with IE isolated from two separate blood cultures, as noted below
    - Viridans streptococci, *Streptococcus bovis*, *Staphylococcus aureus*, or HACEK group
    - Community-acquired enterococci in the presence of a primary focus
  - Microorganisms consistent with IE isolated from persistently positive blood cultures defined as:
    - At least two positive cultures or blood samples obtained >12 hours apart, or
    - All of three, or a majority of four or more separate cultures of blood, the first and last sample obtained > one hour apart
  - Single blood culture positive for *Coxiella burnetii* or an antiphase I Ig antibody titer >1:800
- **Evidence of endocardial involvement**
  - Positive results of echocardiography for IE defined as:
    - Oscillating intracardiac mass on a valve or supporting structures in the path of regurgitant jets or on implanted material in the absence of an anatomic explanation, or
    - Abscess, or
    - New partial dehiscence of a valvular prosthesis
  - New valvular regurgitation (worsening or changing or pre-existing murmur not sufficient)

**Minor Criteria:**

- **Predisposition:** predisposing heart condition or intravenous drug use
- **Fever:** temperature >38°C
- **Vascular phenomena:** major arterial emboli, septic pulmonary infarcts, mycotic aneurysm, intracranial hemorrhage, conjunctival hemorrhages, and Janeway's lesions
- **Immunological phenomena:** glomerulonephritis, Osler's nodes, Roth's spots, and rheumatoid factor
- **Microbiological evidence:** positive blood culture but does not meet a major criterion (as noted above) or serological evidence of active infection with organism consistent with infectious endocarditis.
- **Echocardiographic findings:** consistent with IE but do not meet a major criterion as noted above

If only 1 major and 1-2 minor criteria are fulfilled, or if only 3-4 minor criteria are fulfilled, the event will be coded as "possible endocarditis"

- 2) Evidence of abscess, paravalvular leak, pus, or vegetation confirmed as secondary to infection by histological or bacteriological studies during a re-operation
- 3) Findings of abscess, pus, or vegetation involving the TAV or surgical bioprosthesis at autopsy

### 3.0 Efficacy Event Definitions

PROSTHETIC VALVE DYSFUNCTION	
Stenosis: moderate/severe	Any of the following 1) Peak aortic velocity >4 m/s OR mean aortic gradient >40 mmHg, AND EOA <0.8 cm  . 2) Peak aortic velocity >4 m/s OR mean aortic gradient >40 mmHg, AND EOA ≥0.8 cm  , and DVI <0.25, 3) Peak aortic velocity ≤4 m/s and mean aortic gradient ≤ 40 mmHg, AND EOA <0.8 cm  , and DVI <0.25
Paravalvular regurgitation: moderate	Moderate paravalvular regurgitation (per echo criteria in Table 17, 3 grade scheme)
Paravalvular regurgitation: severe	Severe paravalvular regurgitation (per echo criteria in Table 17, 3 grade scheme) per echo criteria in CIP)
Transvalvular regurgitation: moderate	Moderate paravalvular regurgitation (per echo criteria in Table 17, 3 grade scheme)
Transvalvular regurgitation: severe	Severe transvalvular regurgitation (per echo criteria in Table 17, 3 grade scheme)
Total regurgitation: moderate	Moderate total regurgitation (per echo criteria in Table 16, 3 grade scheme)
Total regurgitation: severe	Severe total regurgitation (per echo criteria in Table 16, 3 grade scheme)

Notes:

1. DVI = Doppler Velocity Index (LVOT VTI/valve VTI)
2. For subjects with BSA <1.6 m^2, the EOA criteria for significant (moderate or severe) stenosis is <0.6 cm^2
3. For subjects with LVOT diameter >2.5 cm, the DVI criteria for significant (moderate or severe) stenosis is <0.2 cm^2
4. Reporting of prosthetic valve dysfunction will be based on core lab results.
5. Prosthetic valve dysfunction events are not reported as adverse events, unless the dysfunction is accompanied with clinical sequelae at the time of event detection, and the clinical sequelae are chronologically and physiologically associated with the dysfunction. However, prosthetic dysfunctions that are associated with adverse events, and that meet the definition of a serious adverse event, should be reported as such.

## 4.0 Event Code List

### Myocardial Infarction

- 100 Peri-procedural myocardial infarction
- 101 Spontaneous myocardial infarction

### Stroke and TIA

- 102 Disabling stroke: ischemic
- 103 Disabling stroke: hemorrhagic
- 104 Disabling stroke: undetermined origin
- 105 Non-disabling stroke: ischemic
- 106 Non-disabling stroke: hemorrhagic
- 107 Non-disabling stroke: undetermined origin
- 108 Transient ischemic attack

### Bleeding Complications

- 110 Life threatening or disabling bleed event
- 111 Major bleeding event
- 112 Minor bleeding event

### Acute Kidney Injury

- 113 Acute kidney injury: stage 1
- 114 Acute kidney injury: stage 2
- 115 Acute kidney injury: stage 3

### Vascular Access and Access Site Complications

#### Major

- 120 Major vascular complication: aortic dissection, aortic rupture, LV perforation, or new apical aneurysm/pseudoaneurysm
- 121 Major vascular complication: access site or access site-related vascular injury (dissection, stenosis, perforation, etc)
- 122 Major vascular complication: distal embolization from vascular source
- 123 Unplanned endovascular or surgical intervention
- 124 New ipsilateral lower extremity ischemia
- 125 Surgery for access site-related nerve injury
- 126 Permanent access site-related nerve injury
- 127 Other major vascular complication

